5.2. Secondary Endpoints

The secondary endpoints planned for this clinical investigation are listed below:

- All AE(s) events during the procedure and through the 14- and 30-days post-procedure will also be assessed, and therefore relationship with the investigational device and/or procedure will be examined by the principal investigator and reported to Rob Surgical
 - Timeframe: Procedure, discharge, 14- and 30 -days follow up visits
- Individual safety (i.e., absence of unwanted injure of any tissue) and performance (VAS scale 0-10 following the subjective surgeon's opinion, being 0 a non-functional tool and 10 an instrument that works exactly equivalent to the surgeon's hands) for each instrument surgical function.
 - Timeframe: Procedure
- Blood Loss defined as estimated mL of blood loss, transfusion rates and use of haemostasis agents
 - Timeframe: Procedure
- Operative Time Procedure measurement for the different tasks.
 - Timeframe: Procedure
- To evaluate post-operative pain in patients through the Cumulative Analgesic Consumption Score (CACS) during the first week (7days) post-procedure.
 - Timeframe: Discharge
- To assess the duration of subject's hospitalization as the Length of Stay (LoS) in hospital calculated from day of admission to day of discharge.
 - Timeframe: Discharge
- Patient pain assessment via VAS. Patient interview questions
 - Timeframe: Discharge, 14- and 30-days post-procedure
- Post-procedure complication rates, including the measurement of the comprehensive complication index (CCI) on a scale from 0 (no complications) to 100 (death), and the Clavien-Dindo classification, which consists of 7 grades (I, II, IIIa, IIIb, IVa, IVb and V), the first one indicating any deviation from the normal postoperative course, the highest-grade indicating death
 - Timeframe: Discharge, 14 and 30 days follow-up

6. SUBJECT SELECTION AND WITHDRAWAL

6.1. Subject Population

This clinical investigation will enroll male and female subjects between 18-90 years old candidates to a radical/simple laparoscopic nephrectomy for benign/malignant pathology.

[REDACTED]

[REDACTED]

6.1.1. Number of Subjects

A total of 3 subjects will be enrolled in the clinical investigation.

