Title: Clinical Investigation Plan. HYROS (HYbrid RObotic Surgery in urology)

Standards and applying chapters: **According to IF-PR01-022 Bitrack_Applicable Regulation and IF-PR01-023_A8 Bitrack Applicable standards**

Protocol Nr: **PL-PR01-027**

[figure not shown]
[figure not shown]
[figure not shown]
[figure not shown]
[figure not shown]
[figure not shown]
[figure not shown]
[figure not shown]
[figure not shown]
[figure not shown]
[figure not shown]
[figure not shown]
[figure not shown]
Revision Nr: **A2**

Date of issue: **04-OCT-2022**

Project Code: **PR01**

Author: **AKRN Scientific Consulting**

REVIEW HISTORY

Reviewed Edition	Date	Section	Rationale	List of Changes
A1	05-Sep-2022	NA	Initial document release	NA
A2	04-Oct-2022	NA	Response to EC comments	Update the version of CIP and date of issue                    
		4		                   
		4.1		                   
		7.1.1		                   
		10.4.1		                   
		13.1		                   

 CONFIDENTIAL
 PL-PR01-027_A2

SUMMARY OF CHANGES

Revision	Summary of Changes
1.0	Document release
2.0	Response to EC comments

CONFIDENTIAL
PL-PR01-027_A2

CONTACT INFORMATION

SPONSOR AND LEGAL MANUFACTURER

Rob Surgical Systems, S.L.

[name]

[REDACTED]

[REDACTED]

Central CRO:

AKRN Scientific Consulting S.L.

[REDACTED]

[REDACTED]

SITE PRINCIPAL INVESTIGATOR:

Hospital Clinic de Barcelona

[REDACTED]

[REDACTED]

[figure not shown]
[figure not shown]
[figure not shown]
[figure not shown]
[figure not shown]
[REDACTED]

CLINICAL INVESTIGATION PLAN (CIP) SUMMARY

Version Number	2.0
Date	04-October-2022
Sponsor	Rob Surgical Systems, S.L. [name]
Clinical Investigation Identification	HYROS
Title	HYbrid RObotic Surgery in urology
Objectives	
The purpose of this early feasibility clinical investigation is to evaluate the safety and feasibility of the Bitrack System and its corresponding ESE and NESE instruments [REDACTED] in patients with the indication of a robot assisted laparoscopic radical/simple nephrectomy.
 
[REDACTED]
 
[REDACTED]

Device Under Investigation	Bitrack System along with its ESE/NESE instruments
Number of Subjects Required for Clinical Investigation	3 subjects shall be included in this early feasibility clinical investigation
Planned Number of Sites	1 investigational site located in Spain

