4. CLINICAL INVESTIGATION DESIGN

The study will be conducted as an early feasibility clinical investigation with a single arm, open-label, and non-randomized design, and will include 3 subjects candidate to a standard of care laparoscopic surgery.

[figure not shown]
The clinical investigation will be conducted in 1 center in Spain. Therefore, this clinical investigation will be considered as monocentric. The site investigation details are provided below:

Hospital Clinic de Barcelona

The objective of the study is to make a preliminary and exploratory evaluation of the safety and performance of the Bitrack System device and its laparoscopic instruments for the first time in humans, 

 Since the study does not include a formal hypothesis and it is an Early Feasibility Study (EFS) as described by Annex I of EN ISO 14155:2020 on Clinical research with medical devices, the statistical analysis of the sample population is not considered applicable.

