4.1. Clinical Investigation Procedures and Follow-up Schedule

The Clinical Investigation visits will occur as in-clinic visits at Baseline, Procedure, Discharge, 14 and 30-days follow-up.

The Flow Chart and the Follow-up phases of this clinical investigation are described in Figure 4-1 below.

[figure not shown]

Figure 4-1. Flowchart of the clinical investigation schedule

The scheduling of the clinical investigation visits will include the following:

Baseline visit (Visit 1)

During the baseline visit, the patient will be informed about the clinical study and provide signed informed consent form if surgeon decides that the patient is eligible as applicable. [REDACTED]
[REDACTED]
[REDACTED]
[REDACTED]

[REDACTED] In case of pregnancy, the patient will withdraw of the study a [REDACTED]
[REDACTED].

Procedure – (Visit 2)

The study population consists of subjects that provided signed ICF, met all inclusion criteria and none of the exclusion criteria, and successfully undergo surgery with the Bitrack System and its corresponding ESE/NESE instruments. These patients will be followed up until 30 days post-procedure. On the other hand, those subjects

in whom robot assisted laparoscopic radical/simple nephrectomy is attempted but not achieved will be followed-up for 30 days, but not included as population for analysis.

For research purposes, we will consider the start of the procedure at the moment of docking, meaning the moment when the camera of the robot is introduced inside the trocar. Therefore, all procedures that started but do not proceed with the use of the Bitrack system or are converted into a conventional laparoscopic/open surgery are included under the Intent-to-treat (ITT) population. Any robot assisted surgery converted to conventional laparoscopic/open surgery due to reasons different than the failure of the Bitrack System and its corresponding sterile endoscopic surgical instruments will be excluded from the endpoint analysis. █

This event will be considered a procedure failure.

CONFIDENTIAL
PI-PR01-027 A2

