6.4. Subject Enrollment

For the HYROS study, a patient is considered enrolled in the clinical investigation from the moment they provide written informed consent, has been confirmed to meet all inclusion criteria and none of the exclusion criteria and has been successfully treated with the Bitrack System.

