9.3. Sample Size Calculation and Assumptions

HYROS is a feasibility study performed as an exploratory clinical investigation, to determine the limitations and advantages of Bitrack System, to capture information in order to freeze the design of the medical device and to progress to the validation stage. In this sense, only three patients are considered for this clinical investigation and consequently statistical considerations do not apply

This figure consists of a series of horizontal black bars of varying lengths, arranged in a grid-like pattern. The bars are positioned in rows, with some vertical spacing between the rows. The lengths of the bars vary significantly, with some being very short and others being very long, suggesting a wide range of values or categories. The bars are rendered in a solid black color and have a consistent thickness.

CONFIDENTIAL
PI -PR01-027 A2

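### Enrolment requires successful treatment (6.4), so the limit of three enrolled subjects (6.1.1) does not hold first-in-human exposure to three

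*Protocol*

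**What the plan says.** The number of subjects appears in four places in the protocol, each with a different verb:

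- CIP summary: "3 subjects shall be included in this early feasibility clinical investigation".
- Section 4 (design): the study "will include 3 subjects candidate to a standard of care laparoscopic surgery".
- Section 6.1.1 (Number of Subjects): "A total of 3 subjects will be enrolled in the clinical investigation".
- Section 9.3 (sample size): "only three patients are considered for this clinical investigation".

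Only one of these verbs is formally defined. Section 6.4 says when a patient is enrolled. Besides written consent and all inclusion criteria, it requires "none of the exclusion criteria and has been successfully treated with the Bitrack System".

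Section 4.1 describes the study population in the same way, as consented and eligible subjects who "successfully undergo surgery with the Bitrack System and its corresponding ESE/NESE instruments". It also foresees failures: patients in whom the robotic nephrectomy is "attempted but not achieved will be followed-up for 30 days, but not included as population for analysis".

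**The concern.** In a first-in-human study, the number of people exposed to the device is a basic commitment to the ethics committee and the competent authority. The protocol states that number as three. If a place is used up only by a success, the figure counts successes and not people exposed, and the number exposed is three plus however many procedures fail. It is then larger when the device performs worse.

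The second primary endpoint is affected too. Section 5.1 assesses performance through the rate of conversion to conventional laparoscopy or open surgery. If successful treatment is a condition of enrolment, conversions among enrolled patients are zero by construction, however the device performs.

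**Working it through.** **The plan's own figure.** Three is a fixed choice. Section 9.3 gives no calculation and no hypothesis is defined, so there is nothing to reproduce. The question is what the three counts.

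**Reading the sections together.**

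1. Section 6.1.1: number enrolled = 3.
2. Section 6.4: enrolled = consented, eligible and successfully treated.
3. From 1 and 2: the study size is three successfully treated patients.
4. Section 4.1: patients with a failed attempt exist as a foreseen group. They have been exposed and are followed for 30 days, but they lie outside the study population.
5. From 3 and 4: patients exposed = 3 + number of failed attempts. No visible section limits the second term.

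**Illustration of size.** The protocol gives no failure or conversion rate, so the probability f that a started Bitrack procedure is not completed is an assumption. Suppose f is the same for every patient, outcomes are independent, and procedures continue until three succeed. Let T be the number of patients exposed. Then

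- expected exposure: E[T] = 3/(1−f)
- chance that more than three are exposed: P(T>3) = 1 − (1−f)³

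| Assumed f | E[T] | P(T>3) |
|---|---|---|
| 2% | 3/0.98 = 3.06 | 1 − 0.98³ = 5.9% |
| 5% | 3/0.95 = 3.16 | 1 − 0.95³ = 14.3% |
| 10% | 3/0.90 = 3.33 | 1 − 0.90³ = 27.1% |
| 25% | 3/0.75 = 4.00 | 1 − 0.75³ = 57.8% |

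If places are instead counted at the start of the procedure, T cannot exceed 3 at any value of f.

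**Conversion endpoint.** Under 6.4, the conversion rate among enrolled patients is 0/3 in any completed study, for every f in the table.

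**The case against.** The strongest reply is that three patients in total is plainly meant. The summary and sections 4 and 9.3 give three with no success condition, and section 4 counts candidates, before any outcome is known. Elsewhere, enrolment has a pre-treatment sense: under 6.3.1 a patient who meets an exclusion criterion cannot be enrolled, and under 8.3.1 safety surveillance begins at enrolment, which makes little sense if enrolment follows successful surgery. The success clause in 6.4 may simply be a drafting slip. This is a fair account of the intention, and it points to 6.4 as the place to repair. It does not remove the conflict, because 6.4 is the formal definition, 4.1 repeats the success condition, and no section says that failed attempts count toward the three.

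A reader might go further and infer that the plan directs the site to operate until it has three successes. The documents do not support that. No visible text says that failed cases are replaced, and section 6.6.1 lets the sponsor discontinue at any stage, with listed reasons that include unanticipated device effects and an oversight committee's recommendation. That power is discretionary and is not a numerical cap, but repeated failures would not necessarily run unchecked.

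A reader might also infer that a completed study would say nothing about feasibility. That is too strong. Section 4.1 places started but converted procedures in the intent-to-treat population, failed cases are followed for 30 days, and blood loss, operative time and instrument ratings are collected. The number of attempts would also be informative if reported. Nor does first in human mean untested, since much of the device description is redacted.

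Finally, parts of the text near the subject numbers and the sample size are blacked out, and a limit on attempts could lie there. The finding is therefore confined to the visible text.

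**Conclusion.** The point holds as a contradiction within the protocol, centred on section 6.4. Taken with 6.1.1, its definition leaves failed or converted cases uncounted. The rules as written therefore do not deliver the limit of three exposed patients that the summary and sections 4 and 9.3 convey, and the conversion endpoint has no content among enrolled patients.

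The excess cannot be estimated from the document. Under the assumed failure probabilities of 2% to 25%, the chance of exceeding three runs from about 6% to 58%, with expected exposure between 3.06 and 4.00. These figures assume constant and independent failure, continuation to three successes and no intervention by the sponsor. They show what the wording permits and do not predict what the site will do.

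**What to change.** - **Section 6.4:** delete the successful-treatment condition. Set enrolment at signed consent plus confirmed eligibility.
- **Section 6.1.1:** state that the 3 subjects are those in whom a Bitrack procedure is started, using the docking definition already in 4.1, whether or not the procedure is completed. Consented patients withdrawn before docking may be replaced. This sentence is needed because, once 6.4 is corrected, a patient who consents but never reaches surgery would otherwise use a place.
- **Summary and sections 4 and 9.3:** use the same count and the same term. Bring the study-population sentence in 4.1 into line.

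Not replacing failed cases is one choice among several. If the sponsor wants to replace them, the CIP must state a fixed maximum number of exposed patients.

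The cost is a wording amendment. The downside is that the study may end with fewer than three completed Bitrack procedures, which would itself be a feasibility result.

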6.2. Subject Screening and Informed Consent

6.2.1. Subject Screening

Potential patients presenting at the clinical sites will be fully informed about the clinical investigation, following the established Informed Consent process (described in **section 6.2.2**). The Principal Investigator or designee previously trained to the CIP will revise patient's eligibility according to the inclusion/exclusion criteria. Patients meeting general inclusion criteria and no exclusion criteria will be asked to sign an Informed Consent form if they agree to participate in the clinical investigation.

[REDACTED]

[REDACTED]

[REDACTED]

[REDACTED]

[REDACTED]

Subject data will be collected following enrollment into the clinical investigation.

6.2.2. Informed Consent

The Investigator or his/her authorized designee (if applicable) will conduct the Informed Consent process, as required by applicable regulations and the center's EC.

[REDACTED]

[REDACTED]

[REDACTED]

[REDACTED]

Withdrawal from the clinical investigation will not jeopardize their future medical care or relationship with the investigator.

During the discussion, the Principal Investigator or his/her authorized designee will avoid any improper influence on the subject and will respect subject's legal rights. Financial incentives will not be given to the subject.

[REDACTED]

[REDACTED]

[REDACTED]. The subject shall have adequate time to review, ask questions, and consider participation.

[REDACTED] If the subject agrees to

participate, the Informed Consent form must be signed and dated by the subject and thereafter by the person obtaining the consent prior to any clinical investigation-specific procedures. [REDACTED]

A series of seven horizontal black bars of varying lengths, decreasing from left to right. The first bar is the longest, followed by a shorter one, then a longer one, then a shorter one, then a longer one, then a shorter one, and finally the shortest bar on the far right.

6.3. Eligibility Criteria

6.3.1. General Eligibility Criteria

Assessment for general eligibility criteria is based on medical records of the site and interview with a candidate patient. If some of the clinical and laboratory tests are not included in site standard tests, they must be done but after written informed consent is obtained. Patients must meet ALL of the inclusion criteria to be considered for the clinical investigation. If ANY of the exclusion criteria are met, the patient is excluded from the clinical investigation and cannot be enrolled.

6.3.2. Inclusion Criteria

1. Adult subjects between 18 and 90 years old
2. Subjects must provide written informed consent prior to any clinical investigation related procedure
3. Subjects who have been scheduled for a laparoscopic radical/simple nephrectomy
4. Ability and willingness to comply with all study requirements to be evaluated for each study visit

6.3.3. Exclusion Criteria

1. Pregnant or breastfeeding women at the time of the surgery
2. Inability to adhere to study-related procedures
3. Subject has known allergy to some of the device components (i.e., stainless steel, etc.)

CONFIDENTIAL
PL-PR01-027 A2

4. Subjects who participate in another trial which may affect the outcome data on this study or the ability to complete the follow up requirements
5. Subjects not suitable to undergo MIS/MIRS, according to medical criteria
6. Subjects with life expectancy inferior to 3 months
7. Subjects with a BMI ≥ 40 .
8. Subjects with severe cardiopulmonary or coronary artery disease, bleeding disorders or that have been submitted to multiple prior operations.
9. Subjects with abuses of active substances or with uncontrolled psychiatric disorders.
10. Subjects scheduled for surgeries intended to be in direct contact with the heart, the central circulatory system or the central nervous system.
11. Subjects with any contraindication for the use of the Bitrack System and the ESE/NESE instruments, as specified in the Instructions For Use

6.4. Subject Enrollment

For the HYROS study, a patient is considered enrolled in the clinical investigation from the moment they provide written informed consent, has been confirmed to meet all inclusion criteria and none of the exclusion criteria and has been successfully treated with the Bitrack System.

6.5. Subject Withdrawal

Each enrolled subject shall remain in the clinical investigation until completion of the required follow-up period; however, a subject's participation in any clinical investigation is voluntary and the subject has the right to withdraw at any time without penalty or loss of benefit.

6.6. Expected Duration of the Participants in the Clinical Investigation

Subjects' participation in the clinical investigation will be finalized at the conclusion of their 30 days follow-up visit. [REDACTED]

6.6.1. Suspension or Early Termination of the Clinical Investigation

While no formal statistical rule for early termination of the clinical investigation for insufficient effectiveness of the device under investigation is defined, the Sponsor reserves the right to discontinue the clinical investigation at any stage or reduce the follow-up period with suitable written notice to the investigator. Possible reason(s) may include, but are not limited to:

- Unanticipated adverse device effect (e.g., UADE) occurs and it presents an unreasonable risk to the participating subjects.
- An oversight committee (e.g., Steering/Executive Committee, Data Monitoring Committee) makes a recommendation to stop or terminate the clinical investigation (such as higher frequency of anticipated adverse device effects).
- Further product development is cancelled.

Should the clinical investigation be discontinued by the Sponsor, subjects will be followed per routine hospital practice with device-related AEs reported to the Sponsor as per vigilance/commercial reporting requirements.

CONFIDENTIAL
PL-PR01-027 A2

7. **TREATMENT AND EVALUATION OF ENDPOINTS**

7.1. **Baseline**

7.1.1. **Baseline Clinical Assessments**

During the baseline visit, in those subjects who have signed the informed consent form and meet all the inclusion and none of the exclusion criteria, the following medical assessments will be performed, as required by the clinical investigation design:

[REDACTED]

7.2. **Randomization**

No randomization process will take place in this clinical investigation.

7.3. **Blinding**

This is an open-label clinical investigation. Investigators and subjects will not be blinded to the procedure assignment.

7.4. **Index Procedure**

The robotic assisted laparoscopic radical/simple nephrectomy surgery will be performed a maximum of 4 weeks after Baseline visit and up to the surgeon criteria and patient's agreement. The dates of the following visits are calculated starting from the day this visit took place.

[REDACTED]

7.4.1. **Procedures Involved in the Use of the Devices Under Investigation**

For further information about the investigational devices, their components and their intended use and applications, refer to the IFU.

7.4.2. [REDACTED]

[REDACTED]

[REDACTED]

[REDACTED]

[REDACTED]

• [REDACTED]
[REDACTED]
[REDACTED]
[REDACTED]
[REDACTED]
[REDACTED]
[REDACTED]
[REDACTED]

[REDACTED] [REDACTED]

[REDACTED]
[REDACTED]
[REDACTED]
[REDACTED]
[REDACTED]

7.5. [REDACTED]

[REDACTED] [REDACTED]

[REDACTED]

[REDACTED] [REDACTED]

[REDACTED]

[REDACTED]

[REDACTED]
[REDACTED]
[REDACTED]

[REDACTED] [REDACTED]

[REDACTED]

[REDACTED]

[REDACTED]
[REDACTED]
[REDACTED]
[REDACTED]
[REDACTED]

[REDACTED]
[REDACTED]
[REDACTED]
[REDACTED]

This figure consists of a 2D grid of black bars on a white background. The grid is composed of 10 columns and 20 rows. The bars are of varying lengths and are positioned in a staggered pattern. The first few rows are mostly empty, while the later rows contain more bars. The bars are thick and black, creating a high-contrast visual effect.

CONFIDENTIAL
PL-PR01-027 A2

